## **Protocol Synopsis**

**Title:** A Double-blind, Randomized, Placebo-controlled, Multicenter Study to Evaluate Safety, Tolerability, and Efficacy of Evolocumab (AMG 145) on LDL-C in Subjects With Type 2 Diabetes Mellitus and Hypercholesterolemia/Mixed Dyslipidemia

**Study Phase:** 3b

**Indication:** Hypercholesterolemia/Mixed Dyslipidemia

**Primary Objective:** To evaluate the effect of 12 weeks of subcutaneous (SC) evolocumab monthly (QM) compared with placebo QM on percent change from baseline in low-density lipoprotein cholesterol (LDL-C) in subjects with type 2 diabetes mellitus and hypercholesterolemia or mixed dyslipidemia on maximally tolerated **dose of** statin of at least moderate-intensity oral daily.

**Secondary Objective(s):** To assess the effects of 12 weeks of SC evolocumab QM compared with placebo QM, in subjects with type 2 diabetes mellitus and hypercholesterolemia or mixed dyslipidemia in combination with maximally tolerated **dose of** statin of at least moderate-intensity oral daily on the following:

- Change from baseline in LDL-C, and percent change from baseline in non-high-density lipoprotein cholesterol (HDL-C), apolipoprotein B (ApoB), total cholesterol (TC), lipoprotein(a) (Lp[a]), triglycerides, HDL-C, and very low-density lipoprotein cholesterol (VLDL-C)
- Percent of subjects attaining LDL-C < 70 mg/dL (1.8 mmol/L)
- Percent of subjects attaining a 50% reduction in LDL-C from baseline

**Safety Objective:** To evaluate the safety and tolerability of SC evolocumab QM compared with placebo QM in subjects with type 2 diabetes mellitus and hypercholesterolemia or mixed dyslipidemia in combination with maximally tolerated **dose of** statin of at least moderate-intensity oral daily.

**Hypotheses:** Subcutaneous evolocumab 420 mg QM in combination with statin once daily will be well tolerated and will result in greater reduction of LDL-C, defined as mean percent change from baseline at weeks 10 and 12 and percent change from baseline at week 12, compared with placebo QM in subjects with type 2 diabetes **mellitus** and hypercholesterolemia or mixed dyslipidemia on maximally tolerated **dose of** statin of at least moderate-intensity daily.

### **Co-primary Endpoints:**

- mean percent change from baseline in LDL-C at weeks 10 and 12
- percent change from baseline in LDL-C at week 12

### **Co-secondary Endpoints:**

For the mean of weeks 10 and 12 and for week 12:

- Tier 1
  - Change from baseline in LDL-C
  - Percent change from baseline in non-HDL-C
  - Percent change from baseline in ApoB
  - Percent change from baseline in TC
  - Achievement of target LDL-C < 70 mg/dL (1.8 mmol/L)
  - LDL-C response (50% reduction of LDL-C from baseline)
- Tier 2
  - Percent change from baseline in Lp(a)
  - Percent change from baseline in triglycerides

- Percent change from baseline in HDL-C
- Percent change from baseline in VLDL-C

**Safety Endpoints:**

- Subject incidence of treatment emergent adverse events
- Safety laboratory values and vital signs at each scheduled assessment

**Study Design:** This is a phase 3b, multicenter, double-blind, randomized, placebo-controlled study designed to assess the efficacy and safety of evolocumab in subjects with type 2 diabetes mellitus with hypercholesterolemia or mixed dyslipidemia.

**Sample Size:** Approximately 400 subjects with type 2 diabetes mellitus with hypercholesterolemia or mixed dyslipidemia.

**Summary of Subject Eligibility Criteria:** The study will enroll adult subjects ( $\geq 18$  years of age) with type 2 diabetes mellitus and elevated LDL-C or non-HDL-C levels on a stable, maximally tolerated statin dose of at least moderate-intensity at signing of the informed consent; statin therapy must remain unchanged during screening and the remainder of the study.

Subjects must have hemoglobin A1c (HbA1c)  $< 10\%$ , must have been receiving pharmacologic treatment for diabetes mellitus for  $\geq 6$  months prior to screening, with stable diabetes therapy prior to randomization to investigational product (IP) and not expected to change throughout the duration of study participation. For a full list of eligibility criteria, please refer to [Section 4.1](#) through [Section 4.1.2](#).

**Investigational Product:** The Amgen investigational medicinal product (IMP) is evolocumab and placebo. The Amgen IP is the IMP plus the device (automated mini-doser [AMD] or prefilled autoinjector [AI]/Pen). In this document, IMP will be referred to as IP.

**Amgen Investigational Product Dosage and Administration:** Evolocumab 420 mg or matching placebo will be administered QM at day 1 and weeks 4 and 8 as an SC injection. The IP is expected to be delivered by AMD but may be achieved by 3 injections with AI/Pen if AMD is not available. Observed, in-clinic dosing should occur at day 1 and week 8  $\pm 3$  days, and subjects will self-administer in an appropriate non-clinic setting (eg, at home) for week 4  $\pm 3$  days.

**Procedures:** The study will consist of 2 periods: the screening/lipid stabilization period and the double-blind treatment period.

After signing the informed consent, subjects will enter a screening period up to 6 weeks including a 4-week lipid stabilization during which their appropriate-dose statin is continued. Subjects are required to be on a stable, maximally tolerated statin of at least moderate-intensity during screening. Screening laboratory tests, including lipid testing, will be conducted during week 2 of screening/lipid stabilization. Subjects must tolerate a SC injection of placebo with device anticipated to be used during the study (either AI/Pen or AMD) prior to randomization.

Subjects who meet all eligibility criteria at the end of the screening/lipid stabilization period will be randomized and initiate their first dose of IP within 5 days of randomization.

During the double-blind treatment period, study visits will occur at day 1, week 8 ( $\pm 3$  days), week 10 ( $\pm 3$  days), and week 12 ( $\pm 3$  days); with baseline evaluations performed on day 1 of treatment before subjects receive the first dose of IP. All subjects will complete a mixed meal tolerance test (MMTT) at the day 1 and week 12 study visits with a baseline and 2-hour ( $\pm 10$  min) postprandial blood collection after the meal. Up to approximately 100 subjects not treated with prandial insulin or glucagon-like peptide-1 agonists will participate in MMTT Extended Timepoints assessments with 3 additional postprandial blood draws at 30 minutes ( $\pm 10$  min), 1 hour ( $\pm 10$  min), and 3 hours ( $\pm 10$  min) after the meal. End of study for all subjects will be at the week 12 ( $\pm 3$  days) visit.

The overall study design is described by a [study schema](#) at the end of this synopsis section. For a full list of study procedures, including the timing of each procedure, please refer to [Section 7](#) and the Schedule of Assessments ([Table 1](#)).

**Statistical Considerations:** The primary analysis will be performed when all randomized subjects in the double-blind treatment period have either completed all scheduled study visits in the double-blind treatment period or have terminated from the study. The superiority of evolocumab to placebo will be assessed for all efficacy endpoints on the full analysis set (FAS), which includes all randomized subjects who receive at least one dose of IP. Methods of adjusting for multiplicity due to multiple endpoints are provided in [Section 10.5.1](#). To assess the co-primary endpoints of the mean percent change from baseline (mean of **screening** week 2 and day 1) in LDL-C at weeks 10 and 12 and the percent change in LDL-C from baseline at week 12, a repeated measures linear effects model will be used on the FAS to compare the efficacy of evolocumab QM with placebo QM. The repeated measures model will include terms for treatment group, stratification factor, scheduled visit and the interaction of treatment with scheduled visit. Analysis of co-secondary endpoints will use the same analysis model as the co-primary endpoints. The co-secondary endpoints of LDL-C response (achievement of LDL-C < 70 mg/dL and achievement of > 50% LDL-C reduction from baseline) will be analyzed using the Cochran-Mantel Haenszel test adjusted by the stratification factor. Safety endpoints will be summarized descriptively by treatment group.

[figure not shown]
**Sponsor: Amgen Inc.**

## Data Element Standards

Version 5/ 20 March 2015

Version(s)/Date(s):

### Study Design and Treatment Schema

EOS=end of study; IP=investigational product; QM=once monthly; SC=subcutaneous

## Study Glossary

Abbreviation or Term	Definition/Explanation
ADE	adverse device effect
AE	adverse event
AI	autoinjector
ALP	alkaline phosphatase
ALT	alanine aminotransferase
AMD	automated mini-doser
ApoA1	apolipoprotein A-I
ApoB	apolipoprotein B
ApoB48	apolipoprotein B48
AST	aspartate aminotransferase
BP	blood pressure
BUN	blood urea nitrogen
CAS	completer analysis set
CHD	coronary heart disease
CK	creatinine kinase
CPK	creatinine phosphokinase
CRF	case report form
CTCAE	Common Terminology Criteria for Adverse Events
CVD	cardiovascular disease
CYP	cytochrome P450
DILI	drug-induced liver injury
DRE	device related event
EDC	electronic data capture
eGFR	estimated glomerular filtration rate
End of Study (end of trial)	defined as the date when the last subject has completed all planned study procedures up to and including the visit as outlined in the Schedule of Assessments
End of Study for Individual Subject	defined as the last day that protocol-specified procedures are conducted for an individual subject or the day the subject withdraws from the study early
End of Treatment	defined as the day a subject receives the last treatment with investigational product before the subject completes the study or ends the treatment early
EOS	end of study
FAS	full analysis set
FBG	fasting blood glucose

Abbreviation or Term	Definition/Explanation
FSH	follicle-stimulating hormone
GCP	Good Clinical Practice
GLP-1	glucagon-like peptide-1
HbA1c	hemoglobin A1c
HCV	hepatitis C virus
HDL-C	high-density lipoprotein cholesterol
ICF	informed consent form
ICH	International Conference on Harmonisation
IFU	Information for Use
IL-6	interleukin-6
IMP	investigational medicinal product
IP	investigational product
IPIM	Investigational Product Instruction Manual
IRB/IEC	institutional review board/independent ethics committee
IVRS	interactive voice response system, telecommunication technology that is linked to a central computer in real time as an interface to collect and process information.
IWRS	interactive web response system
LDH	lactate dehydrogenase
LDL-C	low-density lipoprotein cholesterol
LDLR	low-density lipoprotein receptor
LH	luteinizing hormone
Lp(a)	lipoprotein(a)
MCH	mean corpuscular hemoglobin
MCHC	mean corpuscular hemoglobin concentration
MCV	mean corpuscular volume
MMTT	mixed meal tolerance test
PCSK9	proprotein convertase subtilisin/kexin type 9
PO	orally
PT	prothrombin time
QD	once daily
QM	once monthly
RBC	red blood cells
RDW	red blood cell distribution width
SAE	serious adverse event
SD	standard deviation

Abbreviation or Term	Definition/Explanation
Source Data	information from an original record or certified copy of the original record containing patient information for use in clinical research. The information may include, but is not limited to, clinical findings, observations, or other activities in a clinical trial necessary for the reconstruction and evaluation of the trial. Source data are contained in source documents (original records or certified copies). (ICH Guideline (E6)). Examples of source data include subject identification, randomization identification, and stratification value.
Study day 1	defined as the first day that protocol-specified investigational product(s)/protocol-required therapies is/are administered to the subject
TBL	total bilirubin
TC	total cholesterol
ULN	upper limit of normal
VLDL-C	very low-density lipoprotein cholesterol
WBC	white blood cells

## 1. OBJECTIVES

### 1.1 Primary

- To evaluate the effect of 12 weeks of subcutaneous (SC) evolocumab monthly (QM) compared with placebo QM on percent change from baseline in low-density lipoprotein cholesterol (LDL-C) in subjects with type 2 diabetes mellitus and hypercholesterolemia or mixed dyslipidemia on maximally tolerated **dose of** statin of at least moderate-intensity oral daily.

### 1.2 Secondary

- To assess the effects of 12 weeks of SC evolocumab QM compared with placebo QM, in subjects with type 2 diabetes mellitus and hypercholesterolemia or mixed dyslipidemia in combination with maximally tolerated **dose of** statin of at least moderate-intensity oral daily on the following:
  - Change from baseline in LDL-C, and percent change from baseline in non-high-density lipoprotein cholesterol (HDL-C), apolipoprotein B (ApoB), total cholesterol (TC), lipoprotein(a) [Lp(a)], triglycerides, HDL-C, and very low-density lipoprotein cholesterol (VLDL-C)
  - Percent of subjects attaining LDL-C < 70 mg/dL (1.8 mmol/L)
  - Percent of subjects attaining a 50% reduction in LDL-C from baseline

### 1.3 Safety

- To evaluate the safety and tolerability of SC evolocumab QM compared with placebo QM in subjects with type 2 diabetes mellitus and hypercholesterolemia or mixed dyslipidemia in combination with maximally tolerated **dose of** statin of at least moderate-intensity oral daily.

### 1.4 Exploratory

To describe the effects over time of SC evolocumab QM compared with placebo QM, in subjects with type 2 diabetes mellitus and hypercholesterolemia or mixed dyslipidemia in combination with maximally tolerated statin of at least moderate-intensity oral daily on:

- change from baseline in proprotein convertase subtilisin/kexin type 9 (PCSK9) levels and on change from baseline and percent change from baseline of LDL-C, TC, non-HDL-C, ApoB, VLDL-C, HDL-C, apolipoprotein A-I (ApoA1), triglycerides, and Lp(a)
- change and percent change from baseline on fasting and postprandial plasma laboratory parameters of interest including glucose, insulin, pro-insulin, C-peptide, free fatty acids, glucagon, lipids, chylomicrons, apolipoprotein B48 (ApoB48), interleukin-6 (IL-6), adiponectin after a mixed meal tolerance test (MMTT)
- the relationship between novel and established biochemical cardiovascular and lipid biomarkers and effects of evolocumab
- potential correlations of study data including the subject response to evolocumab with genetic variation in markers of PCSK9 signaling, low-density lipoprotein receptor (LDLR) turnover, cholesterol metabolism, inflammation, and plaque stability in subjects consenting to the optional pharmacogenetic analysis

## 2. BACKGROUND AND RATIONALE

### 2.1 Disease

Cardiovascular diseases (CVD) accounted for over 17 million of these deaths, nearly 80% of which were due to heart attacks and strokes alone (responsible for 7.3 million and 6.2 million deaths, respectively). Type 2 diabetes mellitus is a major independent risk factor for CVD-coronary heart disease (CHD) and stroke, and conditions such as hypertension and dyslipidemia frequently coexist with diabetes ([American Diabetes Association, 2005](#)). Most diabetic patients have an approximately 2-fold increased level of cardiovascular risk compared to nondiabetics, even when established CHD is absent. Patients with type 2 diabetes also have an increased prevalence of lipid abnormalities contributing to the increased risk of cardiovascular disease ([Arca, 2007](#)). Therefore, treatment guidelines recommend aggressive lipid treatment goals for patients with diabetes (eg, [Brunzell et al, 2008](#); [Grundy et al, 2004](#); [Reiner et al, 2011](#); [Chinese Society of Cardiology of Chinese Medical Association, 2011](#)).

A direct correlation between dyslipidemia and cardiovascular-related deaths has been demonstrated across several global regions ([Menotti et al, 2008](#); [Imano et al, 2011](#); [Yang et al, 2012](#)). Because dyslipidemia is a major modifiable risk for the development of CVD, therapies for hyperlipidemia/dyslipidemia can translate into an opportunity for significantly reducing cardiovascular morbidity and mortality throughout different populations and world regions.

### 2.2 Amgen Investigational Product Background

Recycling of the hepatic cell surface LDLR plays a critical role in regulating serum LDL-C levels. Proprotein convertase subtilisin/kexin type 9 binds to the LDLR and down regulates hepatic cell surface LDLR, which, in turn, leads to increased levels of circulating LDL-C. Humans with PCSK9 loss-of-function mutations have cholesterol levels lower than normal and reduced incidence of CHD ([Abifadel et al, 2009](#)).

Evolocumab (formerly referred to as AMG 145) is a fully human monoclonal immunoglobulin G2, developed at Amgen Inc., that specifically binds to PCSK9 preventing its interaction with the LDLR. The inhibition of PCSK9 by evolocumab leads to increased LDLR expression and subsequent decreased circulating concentrations of LDL-C.

Refer to the [Evolocumab Investigator's Brochure](#) for more information on evolocumab.

### 2.3 Rationale

It is anticipated that evolocumab may be used in diabetic individuals who cannot achieve their LDL-C goals despite the use of maximally tolerated statin therapy (Bruckert et al, 2005; Franc et al, 2003). Therefore, it is important to understand the safety and efficacy of evolocumab on the background of statin therapy in diabetic patients.

### 2.4 Clinical Hypotheses

The primary hypothesis of this study is that SC evolocumab 420 mg QM in combination with statin once daily will be well tolerated and will result in greater reduction of LDL-C, defined as mean percent change from baseline at weeks 10 and 12 and percent change from baseline at week 12, compared with placebo QM in subjects with type 2 diabetes and hypercholesterolemia or mixed dyslipidemia on maximally tolerated **dose of statin** of at least moderate intensity daily.

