#### **10.5.4 Safety Endpoints**

The current Medical Dictionary for Regulatory Activities version at the time of the data lock will be used to code all adverse events to a system organ class and a preferred term.

Subject incidence of all treatment emergent adverse events will be tabulated by system organ class and preferred term. Tables of fatal adverse events, serious adverse events, adverse events leading to withdrawal from IP, device-related adverse events, and significant treatment-emergent adverse events will also be provided. Subject incidence of disease-related events and fatal disease-related events will be tabulated by system organ class and preferred term. Subject-level data may be provided instead of tables if the subject incidence is low.

---

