4.2 Planned Covariates

Stratification factor in the double-blind treatment period:

- LDL-C < 130 mg/dL vs ≥ 130 mg/dL

Baseline Characteristics:

- Age
- Sex (male, female)
- Race (black, white, and other)
- LDL-C
- Family history of premature coronary heart disease (CHD) (yes,no)
- PCSK9
- Region (North America, Europe, other)
- Body Mass Index (BMI)
- Hypertension (yes, no)

- Current smoker (yes, no)
- Additional baseline CHD risk factor (yes, no)
- Triglycerides
- Insulin Use (yes, no)
- Statin intensity (High/Moderate/Low intensity as per ACC/AHA guidelines)
- Lipid entry target (above both non-HDL-C and LDL-C entry criteria thresholds, above non-HDL-C entry criteria threshold only, and above LDL-C criteria threshold only)
- Presence of diabetes complications (0 complications, presence of 1 or more complications)

5. Hypotheses and/or Estimations

The primary statistical hypothesis of the co-primary endpoints is as follows:

The null hypothesis is that there is no mean difference in the mean percent change from baseline at weeks 10 and 12 or in the percent change from baseline at week 12 in LDL-C between evolocumab 420 mg QM and placebo, and the alternative hypothesis is that a mean difference does exist.

6. Definitions

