10.6 Safety Analyses

10.6.1 Adverse Events and Disease-Related events

The Medical Dictionary for Regulatory Activities (MedDRA) version 19.0 or later will be used to code all events categorized as adverse events (AEs) or disease-related events (DREs) to a system organ class and a preferred term. Severity of AEs will be graded using the CTCAE ([Appendix B](#)) and recorded on the eCRF. All adverse event tables will

be summarized by actual treatment group. Treatment-emergent adverse events are events with an onset after the administration of the first dose of IP as defined in [Section 6.3](#).

Subject incidence of all treatment-emergent AEs, serious AEs, AEs leading to withdrawal of investigational product, and fatal AEs will be tabulated by system organ class and preferred term in descending order of frequency.

Summaries of treatment-emergent and serious AEs occurring in at least 1% of the subjects by preferred term in any treatment arm will be provided in descending order of frequency.

Subject incidence of DREs will be summarized by system organ class and preferred term for all treatment-emergent DREs and fatal DREs.

Subject incidence of adverse events related to a device will be tabulated by preferred term in descending order of frequency by treatment group.

Subject incidence of adverse events associated with lipid lowering therapies:

- Muscle-related
- Liver-related

associated with injectable protein therapies:

- Injection site reactions
- Hypersensitivity or allergic reactions

and potential hepatitis C infections will be summarized by category and preferred term.

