10.6.2 Laboratory Test Results

Descriptive statistics will be provided for actual values and changes from baseline in select laboratory parameters at each protocol-specified scheduled visit. Laboratory analytes are provided in the protocol [Table 2](#). Lab shift tables using the CTCAE v4.03 or later grading will be used for the select analytes of interest, when applicable.

In addition, CK and liver function test (LFT) abnormalities will be assessed by the incidence overall and by visits of the following categories:

- CK > 5 x ULN
- CK > 10 x ULN
- ALT or AST \geq 3 x ULN
- ALT or AST \geq 5 x ULN

- Total bilirubin $\geq 2 \times$ ULN
- (ALT or AST $\geq 3 \times$ ULN) and (Total bilirubin $\geq 2 \times$ ULN and ALP $< 2 \times$ ULN)

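### Tolerability is part of the primary clinical hypothesis, but no planned safety result could contradict it or say how much excess harm is excluded

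*Protocol*

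**What the plan says.** Protocol 2.4 (Clinical Hypotheses) begins: "The primary hypothesis of this study is that SC evolocumab 420 mg QM in combination with statin once daily will be well tolerated". The same sentence goes on to the greater LDL-C reduction, and the synopsis repeats both parts. The safety objective in Protocol 1.3 is worded as a comparison: "To evaluate the safety and tolerability of SC evolocumab QM compared with placebo QM".

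SAP Section 5 states the statistical hypothesis for the co-primary endpoints only: "The null hypothesis is that there is no mean difference in the mean percent change from baseline at weeks 10 and 12", and likewise for week 12. Tolerability does not appear there.

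For the safety analysis, the synopsis (Statistical Considerations) says: "Safety endpoints will be summarized descriptively by treatment group". Protocol 10.5.4 adds: "Subject incidence of all treatment emergent adverse events will be tabulated by system organ class and preferred term". SAP 10.6.1 says: "Subject incidence of all treatment-emergent AEs, serious AEs, AEs leading to withdrawal of investigational product, and fatal AEs will be tabulated". It also plans a table of the more frequent events ("Summaries of treatment-emergent and serious AEs occurring in at least 1% of the subjects by preferred term in any treatment arm") and incidence tables for muscle-related, liver-related, injection-site and hypersensitivity events.

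The safety plan is wider than adverse events. SAP 10.6.2 has laboratory changes from baseline, shift tables and threshold categories ("CK and liver function test (LFT) abnormalities will be assessed by the incidence overall and by visits of the following categories"), and SAP 10.6.3 has vital signs. All of these are summaries by arm or by visit. Neither document defines what well tolerated means, and neither names a safety margin, a between-arm difference, an interval or a test.

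**The concern.** A hypothesis should be open to contradiction by some planned result. Here the LDL-C part is, and the tolerability part is not: whatever the incidence tables show, the documents contain nothing to set them against.

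The safety objective asks for a comparison with placebo, and the plan supplies the two sides of that comparison without the comparison itself. The study report could state that the drug was well tolerated without stating how large an excess of, say, muscle-related events the data still allow. Under 2:1 allocation the placebo percentages rest on few subjects (3% of 130 is about 4), so two similar percentages are weak evidence of no excess.

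**Working it through.** **1. Set the texts side by side.**

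| Element | LDL-C part | Tolerability part |
|---|---|---|
| Clinical hypothesis (Protocol 2.4, synopsis) | yes | yes |
| Statistical hypothesis (SAP 5) | yes | no |
| Between-arm estimate or test | repeated measures model | none |
| Criterion | two-sided 0.05 on both co-primaries | none |
| Sample size basis (Protocol 10.2, SAP 3.2) | yes | none |

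**2. Reproduce the plan's own figures.** No precision or power is stated for safety, so only the lipid figures can be checked. For HDL-C (effect 5, SD 15, 400 subjects less 5% = 380, split 2:1 into 253.3 and 126.7):

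- SE = 15 × √(1/253.3 + 1/126.7) = 1.632
- Power = Φ(5/1.632 − 1.96) = Φ(1.10) = 0.865, against about 86% stated

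The triglyceride table reproduces as 0.88, 0.78, 0.68 and 0.59 at SD 35, 40, 45 and 50, with 380 subjects split 270:130. The lipid figures are sound. They say nothing about adverse events.

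**3. What the trial could say about an excess.** Inputs are about 270 and 130 subjects (Protocol 3.1). Placebo incidences are assumptions, because the documents give none. I use the Newcombe interval for the difference d = p(evolocumab) − p(placebo), built from the Wilson limits (l, u) of each arm:

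- Wilson limits: [p + z²/2n ± z√(p(1−p)/n + z²/4n²)] / (1 + z²/n), with z = 1.96
- Upper limit of the difference: d + √[(u_evo − p_evo)² + (p_pbo − l_pbo)²]

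Example at about 3%, with 8/270 against 4/130:

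- Evolocumab 2.96% (upper Wilson limit 5.74%); placebo 3.08% (lower Wilson limit 1.20%)
- d = −0.11 points
- Upper limit = −0.11 + √(2.77² + 1.87²) = −0.11 + 3.35 = about +3.2 points

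| Approximate rate | Events (270 vs 130) | 95% upper limit for the excess |
|---|---|---|
| 3% | 8 vs 4 | +3.2 points |
| 5% | 14 vs 7 | +4.1 |
| 10% | 27 vs 13 | +5.8 |
| 40% | 108 vs 52 | +10.0 |

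At about 3% the upper limit exceeds the placebo rate, so equal-looking percentages do not exclude a doubling. At 5% and above it is below the placebo rate, and they do.

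**4. How often a doubling would reach significance.** No such test is planned; this only illustrates precision. The figure is the exact probability, over two independent binomials, that a two-sided Fisher test gives p < 0.05 with the excess on evolocumab:

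| Placebo to evolocumab | Power |
|---|---|
| 2% to 4% | 0.12 |
| 3% to 6% | 0.20 |
| 5% to 10% | 0.36 |
| 6.5% to 13% | 0.48 |
| 7% to 14% | 0.52 |
| 10% to 20% | 0.71 |

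Power crosses one half between placebo rates of 6.5% and 7%.

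**The case against.** Descriptive safety reporting is usual in a 12-week lipid trial of 400 subjects, and it is not an error. Section 2.4 is headed as clinical hypotheses, SAP 5 states the statistical one separately, and the safety endpoints are listed apart from the primary endpoints and outside the multiplicity scheme. In the sentence in 2.4, the comparison with placebo attaches most naturally to the LDL-C reduction. By-arm incidences on a defined analysis set also let any reader compute a difference and an interval.

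Most of this stands. It shows that no inferential safety claim was set up and that the co-primary analysis is untouched. It does not remove the mismatch. The word primary covers both halves of the sentence, and Protocol 1.3 is comparative whatever the grammar of 2.4. An interval that a reader could compute is also different from one that the plan commits the report to use when it concludes on tolerability.

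Three stronger readings are tempting and are not supported:

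- **A doubling of common harms would usually go unseen.** The reverse holds as events become more common: power is 0.71 at a placebo rate of 10%. A non-significant difference is also not unseen, since both rates would stand in the table.
- **The sponsor will infer tolerability from a non-significant test.** Neither document states such a rule or plans such a test.
- **Only adverse events are tabulated.** Laboratory, CK, liver-test and vital-sign summaries are planned too, all of them descriptive.

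**Conclusion.** The point holds as a mismatch between the claim and the analysis. Tolerability sits in the primary clinical hypothesis and the safety objective is comparative, yet nothing planned could contradict the claim or bound the excess harm.

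The textual part needs no assumption. The size does: it rests on about 270 and 130 treated subjects and on assumed placebo incidences. On that basis, near-equal rates would leave an excess of roughly 3 to 6 points open for events at 3% to 10%, and about 10 points for events at 40%. A doubling would more often than not miss significance only for events with a placebo rate below about 7%. The change is worth making because it is cheap and lets the trial answer its own safety objective; it is not a flaw in the efficacy inference.

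**What to change.** 1. In SAP 10.6.1, add the evolocumab-minus-placebo difference in subject incidence with a two-sided 95% confidence interval (for example Miettinen-Nurminen or Newcombe). Do this for any treatment-emergent event, serious events, events leading to withdrawal of investigational product, and the muscle-related, liver-related, injection-site and hypersensitivity categories. Word the tolerability conclusion from these intervals, stating the excess not excluded. No margin, test or multiplicity adjustment is needed.
2. In Protocol 2.4 and the synopsis, limit the primary hypothesis to LDL-C so that it matches SAP 5, and state tolerability as an estimation objective.

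The cost is a few extra table columns and a revised hypothesis sentence in two places, with no new data or subjects. The downside is a less categorical tolerability statement, because the intervals will be wide for uncommon events relative to their rates.
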